Secondary Objectives Assessed at the Month 18 Interim Analysis (All Subjects)	
Improvement of fibrosis by at least 1 stage AND/OR resolution of NASH, without worsening of either	A reduction in fibrosis stage of at least 1 with no increase in hepatocellular ballooning, lobular inflammation or steatosis from baseline based on liver biopsy using NASH CRN criteria AND/OR NASH resolution defined as the overall histopathologic interpretation of 1) "no fatty liver disease" or 2) "fatty liver disease (simple or isolated steatosis) without steatohepatitis" AND a NAS of 0 for ballooning and 0-1 for inflammation with no increase in fibrosis stage from baseline based on liver biopsy using NASH CRN criteria
No worsening of fibrosis AND no worsening of NASH	No increase from baseline in fibrosis stage AND no increase in hepatocellular ballooning, lobular inflammation, or steatosis based on liver biopsy using NASH CRN criteria
Improvement in each key histological feature of NASH	A reduction in score of at least 1 from baseline for steatosis, lobular inflammation, or hepatocellular ballooning based on liver biopsy using NASH CRN criteria
Improvement of fibrosis by at least 2 stages	A reduction from baseline in fibrosis of at least 2 stages at Month 18 based on liver biopsy using NASH CRN criteria
Improvement in NAS by at least 2 points with no worsening of fibrosis	A reduction in NAS by at least 2 points with no increase in fibrosis stage from baseline based on liver biopsy using NASH CRN criteria
Improvement of fibrosis and resolution of NASH as a composite endpoint and as defined by both endpoints being met in the same subject	A reduction from baseline in fibrosis stage of at least 1 and resolution of NASH as defined above
Resolution of fibrosis	A fibrosis stage of 0 based on liver biopsy using NASH CRN criteria
Histological progression to cirrhosis	A fibrosis stage of 4 based on liver biopsy using NASH CRN criteria
Liver biochemistry and markers of liver function	ALT, AST, GGT, ALP, total and direct bilirubin, albumin, INR, and platelets

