16.6.3. Responder Endpoints

For the analyses of the primary and key secondary histological efficacy endpoints, in which subjects are classified as either a responder or a non-responder (binary outcome), any subject who does not provide any assessment at the specified timepoint and after baseline for the defining of response will be considered to be a non-responder. That is, for the percentage of responders, the subject will be included in the denominator and will not contribute to the numerator. Subjects who early terminate before Month 18, biopsy results at the time of early termination, if available, will be included in Month 18 histological endpoints analyses.

A completer analysis will also be conducted, excluding those subjects who do not provide an assessment at the specified timepoint for the defining of response. That is, for the percentage of responders, the subject will not be included in the numerator or the denominator.

Additional sensitivity analysis will be described in the SAP.

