#### Secondary Endpoints:

- Percentage of subjects with no worsening of fibrosis AND no worsening of NASH
- Percentage of subjects with progression to cirrhosis
- Percentage of subjects with improvement of fibrosis by at least 2 stages
- Percentage of subjects with improvement of each key histological feature of NASH by at least 1 point (steatosis, lobular inflammation, and hepatocellular ballooning)
- Percentage of subjects with improvement of NAS by at least 2 points with no worsening of fibrosis
- Percentage of subjects with improvement of fibrosis and resolution of NASH as a composite endpoint and as defined by both endpoints being met in the same subject
- Percentage of subjects with resolution of fibrosis

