### 2.3.2.2. Secondary Efficacy Endpoints

#### 2.3.2.2.1. Histological Analysis

The analysis of the histological efficacy endpoints at End of Study will be based on the following endpoints analyzed for all post-baseline biopsies.

- Percentage of subjects with Improvement of fibrosis by at least 1 stage with no worsening of NASH
- Percentage of subjects with Resolution of NASH with no worsening of fibrosis

- Percentage of subjects with improvement of fibrosis by at least 1 stage AND/OR resolution of NASH, without worsening of either
- Percentage of subjects with no worsening of fibrosis AND no worsening of NASH
- Percentage of subjects with histological progression to cirrhosis
- Percentage of subjects with improvement of fibrosis by at least 2 stages
- Percentage of subjects with improvement of each key histological feature of NASH by at least 1 point (steatosis, lobular inflammation, and hepatocellular ballooning)
- Percentage of subjects with improvement of NAS by at least 2 points with no worsening of fibrosis
- Percentage of subjects with improvement of fibrosis and resolution of NASH as a composite endpoint and as defined by both endpoints being met in the same subject
- Percentage of subjects with resolution of fibrosis

[figure not shown]

[figure not shown]

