Panel A of 3 pathologists will read images of slides stained with H&E to characterize NAS (ballooning, inflammation, steatosis) score and Panel B pathologists will read images of slides stained with Trichrome to characterize NAS CRN fibrosis score. The endpoint regarding the improvement or worsening of fibrosis stage and NASH will be derived based on the results from the consensus values at baseline and any post-baseline liver biopsy collection.

For the analyses of histological efficacy endpoints, in which subjects are classified as either responders or non-responders (binary outcome), any subject who discontinues from the study prior to the Month 18 biopsy Visit and does not have a post-baseline biopsy assessment will be considered a non-responder. Biopsies collected for subjects who discontinued treatment before the Month 18 visit will be included in the Month 18 Interim Analysis of histological endpoints regardless of the timing of the biopsy.

Similar conventions and statistical methodologies will be used for analyses of other exploratory histological-based responder analyses. Responder endpoint analyses will be carried out for the primary and secondary endpoints using the ITT, mITT, Full Efficacy Analysis Population and PP Populations.

A complete summary and description of the analysis plan and populations for histological data based on the consensus method can be found in SAP Addendum V2 (dated 25 Apr 2022).

[figure not shown]

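### The non-responder rule for missing biopsies makes no exception for progression to cirrhosis, where it would favour the arm with more missing biopsies

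*SAP*

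**What the plan says.** SAP 6.2.2 sets the missing-biopsy rule for histological efficacy endpoints that classify each subject as responder or non-responder. It applies to "any subject who discontinues from the study prior to the Month 18 biopsy Visit" and who "does not have a post-baseline biopsy assessment will be considered a non-responder". The same section states: "Responder endpoint analyses will be carried out for the primary and secondary endpoints".

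The Month 18 secondary endpoints in SAP 2.3.1.2 and 6.4.5 include "Percentage of subjects with progression to cirrhosis". The end-of-study list in SAP 2.3.2.2.1 includes "Percentage of subjects with histological progression to cirrhosis", and SAP 6.4.5 adds that all Month 18 histological endpoints will be analysed again at end of study. The protocol synopsis defines the event as "A fibrosis stage of 4 based on liver biopsy using NASH CRN criteria". It is the only endpoint in these lists for which being counted is a bad result.

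Protocol 16.6.3 gives the only explicit arithmetic for a non-responder: "the subject will be included in the denominator and will not contribute to the numerator". It confines that rule to the primary and key secondary histological endpoints. Progression to cirrhosis is neither; the SAP names a single key secondary endpoint, the combined fibrosis improvement and/or NASH resolution endpoint.

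**The concern.** For an improvement endpoint, keeping a subject without a biopsy in the denominator and out of the numerator is conservative, because missing data lower the success rate. For progression to cirrhosis the numerator is the harm, so the same step lowers the harm rate. A rule that is cautious for every other listed endpoint becomes lenient for this one.

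The SAP widened the scope from primary and key secondary endpoints to secondary endpoints generally. It did not say what a non-responder is when the event is unfavourable. The direction of the imputation is left to whoever programs the table, and the two possible readings bias the comparison in opposite directions.

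Missingness may also be related to the outcome. Protocol 9.9.7 and 13.1 allow scheduled biopsies to be omitted after a potential liver-related outcome, and protocol 7.4.2 says that ascites, encephalopathy or variceal haemorrhage may make a confirmatory biopsy unnecessary. A subject who decompensates and leaves before Month 18 without a biopsy could then be tabulated as not having progressed histologically.

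**Working it through.** The documents give no progression rate and no missing-biopsy rate by arm, so there is no figure of the plan's own to reproduce. What follows is an illustration on stated assumptions.

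**Inputs from the documents.** Allocation is 1:1:1 (SAP 2.2.3). The minimum Month 18 stage 2/3 cohort is 750, so 750/3 = 250 per arm. The planned stage 2/3 population is 2085, so 2085/3 = 695 per arm (both totals from SAP 2.2.1).

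**Assumptions.** True progression risk p is the same in both arms (5%, 10% or 15%). The fraction d of subjects covered by the rule is 15% on placebo and 15%, 20%, 25% or 35% on OCA. Missingness is unrelated to progression.

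**Formulas for the observed risk.**
- Missing = no progression: p(1 − d). The ratio is (1 − d_OCA)/(1 − d_placebo), whatever the value of p.
- Missing = progression: d + p(1 − d).
- Biopsied subjects only: p.

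**Worked case, p = 10%, missing 25% OCA versus 15% placebo.**
- Missing = no progression: OCA 0.10 × 0.75 = 7.5%; placebo 0.10 × 0.85 = 8.5%. The difference is −1.0 point and the ratio 0.75/0.85 = 0.88, favouring OCA.
- Missing = progression: OCA 0.25 + 0.075 = 32.5%; placebo 0.15 + 0.085 = 23.5%. The difference is +9.0 points, against OCA.
- Biopsied subjects: 10% versus 10%, no difference.

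**Range under missing = no progression (placebo missing 15%).** The last two columns give the chance of a nominal two-sided 0.05 result in favour of OCA when there is no true effect. They use the pooled-variance two-proportion normal approximation, unstratified, in place of the stratified CMH test. The correct value is 2.5%. Triplets are for p = 5%, 10%, 15%.

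| OCA missing | Ratio | Difference, points | 250 per arm | 695 per arm |
|---|---|---|---|---|
| 15% | 1.00 | 0 | 2.5% | 2.5% |
| 20% | 0.94 | −0.25, −0.50, −0.75 | 3.4, 3.9, 4.4% | 4.2, 5.2, 6.2% |
| 25% | 0.88 | −0.5, −1.0, −1.5 | 4.7, 6.1, 7.4% | 6.9, 10.1, 13.6% |
| 35% | 0.76 | −1.0, −2.0, −3.0 | 8.5, 13.3, 18.4% | 16.4, 29.3, 42.5% |

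**The case against.** The strongest reply is that neither document says a missing biopsy counts as no progression. The protocol's arithmetic does not reach this endpoint, and the SAP's term could be read as the unfavourable outcome. That is correct, and the result above is therefore an inference from the only arithmetic available. The alternative reading is no safer: in the worked case it produces a nine-point artefact against OCA.

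Several limits on scope and size also stand:
- The rule covers only subjects who left the study before the Month 18 biopsy visit without a biopsy. SAP 6.2.2 says that those who stop treatment but stay on study still have a Month 18 biopsy, and that early biopsies count whatever their timing. Protocol 9.9.7 drops the routine Month 18 biopsy for subjects randomized on or after 16 July 2017 who had not had one; those still on study are not covered by the rule.
- SAP 2.3.2.2.1 says the end-of-study endpoints are analysed for all post-baseline biopsies. This may already mean an observed-biopsy basis, but it does not set the denominator or disapply 6.2.2.
- The endpoint is outside the testing sequence in SAP 6.3.1. The end-of-study composite (SAP 6.4.4.2) and the component analysis (SAP 6.4.7.1) are time-to-event, with event-free subjects censored.
- Protocol 16.6.3 plans a completer analysis, though within a section whose rule is limited to primary and key secondary endpoints. The Month 18 per-protocol population requires a biopsy.
- SAP section 1 says the Month 18 analyses were done for the original submission, so a wording change can help only the end-of-study analysis.
- The text of SAP 6.2.3 (Sensitivity Analyses) does not appear in the released document, and SAP Addendum V2, which covers consensus-read histology, is separate. Either may deal with this.

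These points reduce the importance of the gap. They do not close it, because the wording of 6.2.2 still reaches the endpoint and it is listed again for end of study.

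**Conclusion.** The point holds in a limited form. SAP 6.2.2 applies its rule to binary histological endpoints including secondary ones, with no visible exception for progression to cirrhosis. Under the protocol's arithmetic the covered subjects would count as not progressed. If they are more frequent on OCA, the comparison is biased in its favour by about 1 point (ratio 0.88) at an assumed 10% risk and 25% versus 15% missing. The bias in the ratio vanishes if missingness is equal. The size rests on assumed rates, and the model treats missingness as unrelated to progression.

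A reader might infer three stronger conclusions that the documents do not support. The first is that the plan explicitly scores every missing biopsy as no progression; the SAP is silent on direction and covers only the subset described. The second is that OCA 25 mg will have more missing biopsies. Dose-related pruritus (protocol 5.4.2), with discontinuation required at Grade 3 or above (protocol Table 4), makes that plausible, but no by-arm rate is given. The third is that the main outcome result is at risk; it is not, because the effect is confined to a non-key secondary percentage. No claim is made that sensitivity analyses are absent.

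**What to change.** In SAP 6.2.2, exempt progression to cirrhosis from the non-responder rule. For the end-of-study analysis, report the percentage among subjects with a post-baseline biopsy, show missing biopsies by arm, and give both bounds (missing = no progression and missing = progression) as sensitivity analyses. Align the scope of SAP 6.2.2 with protocol 16.6.3, so that both name the same endpoints.

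The cost is a few lines of SAP text and one small table. The biopsied-subject estimate is not a full ITT estimate and is unbiased only if missingness is unrelated to progression. That is why both bounds belong beside it, and why neither bound should serve as the main estimate.

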## **6.3. Control of Type I Error**

### **6.3.1. Histological Primary Endpoints:**

The 2-sided Type I error (alpha) allocated to all testing in this single study will be 0.05. The histological endpoints at the Month 18 Interim analysis will be performed with an alpha level of 0.02. The primary clinical outcomes composite endpoint will be tested with an alpha level of 0.03 which may be augmented by recycled alpha from the Month 18 Interim Analysis.

As shown in [Figure 2](#), the inferential testing will start with the two primary endpoints in comparing the OCA 25 mg dose group versus placebo using the Truncated-Hochberg procedure (Gamma=0.1) and Type I error of 0.02.

**Figure 2: Statistical Testing for the Month 18 Interim Analysis**

All Tests using Truncated Hochberg with gamma=0.1

**I) Scenario 1: Both Primary Endpoints Achieve Statistical Significance at the OCA 25 mg Dose Level**

- a. **Primary Endpoints at the OCA 25 mg Dose Level:** Placebo and OCA 25 mg groups will be compared with respect to the fibrosis and NASH primary efficacy endpoints, using the Truncated-Hochberg procedure, with critical values of 0.011 and 0.01 against which the larger and smaller P-value are to be compared respectively. If the larger P-value is less than 0.011 then both primary efficacy endpoints achieve statistical significance in favor of the OCA 25 mg group. Consequently, the full alpha fraction is preserved and will be carried to compare placebo and OCA 10 mg groups with respect to the primary endpoints using the Truncated-Hochberg procedure (Gamma = 0.1).
- b. **Primary Endpoints at the OCA 10 mg Dose Level:** Placebo and OCA 10 mg groups will be compared, using the Truncated Hochberg procedure, with respect to the fibrosis and NASH primary efficacy endpoints with critical values of 0.011 and 0.01 against which the larger and smaller P-value are to be compared respectively.
- c. **Key Secondary Endpoint at the OCA 25 mg Dose Level:** Placebo and OCA 25 mg groups will be compared with respect to the key secondary endpoint sequentially after the primary endpoint at OCA 10 mg dose level.
- d. **Key Secondary Endpoint at the OCA 10 mg Dose Level:** Placebo and OCA 10 mg groups will be compared with respect to the key secondary endpoint sequentially after the key secondary endpoint at OCA 25 mg dose level.

## **II) Scenario 2: One Primary Endpoint Achieves Statistical Significance at the OCA 25 mg Dose Level**

- a. **Primary Endpoints at the OCA 25 mg Dose Level:** If the larger P-value is greater than 0.011 but the smaller P-value is  $< 0.01$  then only one of the two primary efficacy endpoints achieves statistical significance in favor of the OCA 25 mg group. Preserved alpha of 0.009 will be carried to compare placebo and OCA 10 mg groups with respect to the primary endpoints using the Truncated Hochberg procedure ( $\Gamma = 0.1$ ).
- b. **Primary Endpoints at the OCA 10 mg Dose Level:** Placebo and OCA 10 mg groups will be compared, using the Truncated Hochberg procedure, with respect to the fibrosis and NASH primary efficacy endpoints with critical values of 0.00495 and 0.0045 against which the larger and smaller P-value are to be compared respectively.
- c. **Key Secondary Endpoint at the OCA 25 mg Dose Level:** Placebo and OCA 25 mg groups will be compared with respect to the key secondary endpoint sequentially after the primary endpoint at OCA 10 mg dose level.
- d. **Key Secondary Endpoint at the OCA 10 mg Dose Level:** Placebo and OCA 10 mg groups will be compared with respect to the key secondary endpoint sequentially after the key secondary endpoint at OCA 25 mg dose level.

### **6.3.2. End of Study Primary Endpoints:**

For the analyses of the clinical outcomes composite endpoint at the End of Study, OCA doses will be compared to placebo in a sequential closed gate-keeping manner using Type I error of 0.03.

- First placebo and OCA 25 mg will be compared with respect to the clinical outcomes composite endpoint. If the comparison achieves statistical significance at the 2-sided alpha level in favor of OCA 25 mg, then
- Placebo and OCA 10 mg will be compared with respect to the clinical outcomes composite endpoint.

The possible scenarios of testing the End of Study, depending on Month 18 Interim Analysis results, are provided in [Table 4](#).

**Table 4: End of Study Type 1 Error**

Month 18 Interim Analysis				End of Study		
OCA 25 mg		OCA 10 mg		Testing for Clinical Outcomes Endpoint		
Primary Endpoints		Primary Endpoints				
$\alpha$	Achieve Statistical Significance	$\alpha$	Achieve Statistical Significance	$\alpha$ Clinical Outcomes	Both Dose Groups Hierarchal *	Only OCA 10 mg**
0.02	Both	0.02	Both	0.05	OCA 25 mg →10 mg at $\alpha=0.05$	OCA 10 mg at $\alpha=0.05$
			Only one	0.039	OCA 25 mg →10 mg at $\alpha=0.039$	OCA 10 mg at $\alpha=0.039$
	Only one	0.009	Both	0.039	OCA 25 mg →10 mg at $\alpha=0.039$	OCA 10 mg at $\alpha=0.039$
			Only one	0.03405	OCA 25 mg →10 mg at $\alpha=0.03405$	OCA 10 mg at $\alpha=0.03405$

$\alpha$  for Clinical Outcomes endpoint is 0.03 + carried alpha from the Month 18 Interim Analysis depending on the statistical success of primary endpoints at OCA 25 mg and OCA10 mg dose level

\* Following Month 18 Interim Analysis, both OCA arms are continued for Clinical Outcomes.

\*\* Following Month 18 Interim Analysis, only the OCA 10 mg arm is continued for Clinical Outcomes.

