16.3. Efficacy Analysis at Month 18 Interim Analysis

16.3.1. Primary Efficacy Analysis

All efficacy analysis will be conducted using the ITT population (only including fibrosis stage 2 and stage 3 subjects). The hypothesis testing of primary and (key) secondary endpoints will be conducted with control of Type 1 error (OCA 25 mg, then 10 mg). The 2-sided alpha allocated to all testing in this single study will be 0.05. The histological endpoints will be tested at the Month 18 Interim Analysis with an alpha level of 0.02. The primary clinical outcomes endpoint will be tested with a minimum alpha level of 0.03, and this may be augmented by recycled alpha from the Month 18 Interim Analysis. Adjustments for multiplicity are specified in [Section 16.7](#), and additional details on the testing will be provided in the SAP.

The primary endpoints at the Month 18 Interim Analysis are:

- Improvement in fibrosis by 1 stage or more, with no worsening of hepatocellular ballooning, no worsening of lobular inflammation and no worsening of steatosis
- NASH resolution with no worsening of fibrosis

The primary efficacy analysis for fibrosis improvement at the Month 18 Interim Analysis will test the following hypotheses using the ITT population (the ITT population for the Month 18 Interim Analysis is not the same as that for the overall study and is defined in the SAP):

- H₀₁: The percentage of subjects with fibrosis improvement by 1 stage or more, no worsening of hepatocellular ballooning, and no worsening lobular inflammation is equal between placebo and OCA.
- H₁₁: The percentage of subjects with fibrosis improvement by 1 stage or more, no worsening of hepatocellular ballooning, and no worsening lobular inflammation is different between placebo and OCA.

The primary efficacy analysis for the resolution of NASH with no worsening of fibrosis at Month 18 Interim Analysis will test the following hypotheses using the ITT population:

- H₀₂: The percentage of subjects with NASH resolution and no worsening of fibrosis is equal between placebo and OCA.
- H₁₂: The percentage of subjects with NASH resolution and no worsening of fibrosis is different between placebo and OCA.

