16.7. Multiple Comparisons/Multiplicity

The 2-sided alpha allocated to all testing in this single study will be 0.05. The histological endpoints will be tested at the Month 18 Interim Analysis with alpha level of 0.02. The primary clinical outcomes endpoint will be tested with a minimum alpha level of 0.03, which may be augmented by recycled alpha from the Month 18 Interim Analysis. Further details are provided in the SAP.

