16.7.1. Multiplicity Adjustment for the Month 18 Interim Analysis

For the Month 18 Interim Analysis, testing methods to control overall Type 1 error will be implemented. The sequential testing order will be: primary endpoints in 25 mg versus placebo, followed by primary endpoints in 10 mg versus placebo; details will be provided in the SAP.

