## 1. INTRODUCTION

This document outlines the statistical methods to be implemented for the Month 18 Interim Analysis and End of Study Analysis of Study 747-303 (Phase 3 data collected within the scope of the Intercept Pharmaceuticals, Inc. [the Sponsor], sponsored protocol). Access to unblinded analyses is specified in the data access plan (DAP) and Unblinding Plan (24 Mar 2022). Any deviations from the methods specified in this Statistical Analysis Plan (SAP) will be documented in the clinical study report (CSR).

On 26 Jun 2020, the Food and Drug Administration (FDA) issued a Complete Response Letter (CRL) to New Drug Application (NDA) 212833. Resolution of deficiencies outlined in the CRL required additional histological and safety analyses, which are outlined in SAP Addendum V2.0 (Dated 25 Apr 2022).

It is important to note that all analyses following the CRL that were used to support a re-submission are described in the SAP addendum dated 25 Apr 2022. The Month 18 Interim Analyses that refer to sections in this document ([Section 2.1.1](#), [Section 2.3.1](#), [Section 3.4.1](#)) were done for the original NDA submission. The updates in this SAP document are relevant to End of Study analyses.

Key changes in this document compared to SAP V1.0 (dated 24 Jan 2019) are summarized in [Section 11](#).

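### In the four listed rows of SAP Table 4 the Month 18 primaries and clinical outcomes already use the whole 0.05, so the Month 18 key secondary tests have no alpha and should be labelled nominal

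*SAP*

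**What the plan says.** SAP 6.3.1 opens with a single budget: "The 2-sided Type I error (alpha) allocated to all testing in this single study will be 0.05". Of this, 0.02 goes to Month 18 histology and 0.03 to the clinical outcomes composite. Protocol 16.7 agrees, with the composite "tested with a minimum alpha level of 0.03, which may be augmented by recycled alpha from the Month 18 Interim Analysis".

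At Month 18 the two primaries are tested at 25 mg and then at 10 mg by truncated Hochberg with gamma 0.1. In both scenarios of SAP 6.3.1, item c then has placebo and 25 mg "compared with respect to the key secondary endpoint sequentially after the primary endpoint at OCA 10 mg dose level", and item d does the same for 10 mg after that. Protocol 16.3.1 states that the "hypothesis testing of primary and (key) secondary endpoints will be conducted with control of Type 1 error".

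Table 4 in SAP 6.3.2 gives the outcomes alpha for four combinations of primary success (25 mg/10 mg): both/both 0.05, both/one 0.039, one/both 0.039, one/one 0.03405. Its footnote makes the carried part vary "depending on the statistical success of primary endpoints at OCA 25 mg and OCA10 mg dose level". The key secondary does not appear in it.

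Protocol 16.7.1 gives the Month 18 order as "primary endpoints in 25 mg versus placebo, followed by primary endpoints in 10 mg versus placebo; details will be provided in the SAP". The SAP Introduction says that the Month 18 analyses "were done for the original NDA submission. The updates in this SAP document are relevant to End of Study analyses".

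**The concern.** The alpha left after the Month 18 primaries appears to be committed twice: to clinical outcomes through Table 4, and to the key secondary tests that follow the primaries in the same controlled sequence. If so, the 0.05 budget over all testing is not met as written. A Month 18 key secondary claim and an outcomes claim at recycled alpha could not then both be presented as controlled at 0.05.

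**Working it through.** **Inputs.** From SAP 6.3.1: total 0.05, histology 0.02, outcomes base 0.03, gamma 0.1. From Table 4: the four outcomes alphas.

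**Plan's own figures first.** For two hypotheses at level a, the larger p-value is compared with a × (0.1 + 0.9/2) = 0.55a and the smaller with a/2. With one primary unrejected, 0.55a is used and 0.45a is left. With both rejected, nothing is used. With neither rejected, all of a is used.

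- a = 0.02: critical values 0.011 and 0.01; left after one success 0.45 × 0.02 = 0.009.
- a = 0.009: critical values 0.00495 and 0.0045; left after one success 0.45 × 0.009 = 0.00405.

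These match SAP 6.3.1 and reproduce Table 4:

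| Row (25 mg/10 mg) | Used at 25 mg | Used at 10 mg | Left, r | Outcomes, 0.03 + r | Used + outcomes |
|---|---|---|---|---|---|
| 1 both/both | 0 | 0 | 0.02 | 0.05 | 0.05 |
| 2 both/one | 0 | 0.011 | 0.009 | 0.039 | 0.05 |
| 3 one/both | 0.011 | 0 | 0.009 | 0.039 | 0.05 |
| 4 one/one | 0.011 | 0.00495 | 0.00405 | 0.03405 | 0.05 |

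Nothing remains for the key secondary in any row.

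**Rows not listed.** No primary met at 25 mg: 0.02 + 0.03 = 0.05. Both at 25 mg, none at 10 mg: 0.02 + 0.03 = 0.05. One at 25 mg, none at 10 mg: 0.011 + 0.009 + 0.03 = 0.05. Here r = 0, nothing is carried and there is no breach.

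**Upper bound by key secondary level.** The readable text gives no level (Figure 2 is not shown), so levels are assumed. In row 1, 0.001 gives 0.051, 0.005 gives 0.055, 0.01 gives 0.060 and 0.02 gives 0.070. If the level is r, rows 1 to 4 give 0.070, 0.059, 0.059 and 0.05405. With independent tests these become 0.069, 0.058, 0.058 and 0.053; row 1, for example, is 1 − 0.98 × 0.95 = 0.069.

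**Simulated error.** The key secondary is the union of the two primaries, so its null restricts the rates: fibrosis + NASH − both must be equal on placebo and OCA. All rates below are assumptions; none comes from the documents. There were 400,000 trials per case, 250 and 300 per arm, a shared placebo, the same rates at both doses, unstratified two-proportion z-tests in place of the stratified CMH test, a null outcomes effect independent of histology, and the key secondary at r.

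| Fibrosis/NASH/both %, placebo to OCA | Error with key secondary | Without |
|---|---|---|
| 20/15/5 to 24/18/12 | 0.032 | 0.030 |
| 20/15/5 to 25/20/15 | 0.034 | 0.030 |
| 20/15/2 to 29/24/20 | 0.042–0.044 | 0.034–0.036 |
| 20/15/5 to 28/15/13 | 0.043 | 0.042 |
| 12/8/2 to 18/12/12 | 0.036–0.037 | 0.032 |
| 25/15/5 to 35/25/25 | 0.044–0.046 | 0.035–0.038 |
| 20/15/2 to 33/30/30 | 0.054–0.056 | 0.045–0.046 |
| 20/20/0 to 40/40/40 | 0.065–0.069 | 0.050 |

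Only the last two exceed 0.05. They need almost no overlap of the two responses on placebo and complete overlap on OCA. A correlation of 0.3 between the outcomes and key secondary statistics lowers them by at most 0.002.

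**The case against.** The strongest reply is that the key secondary is only ordered after the primaries and takes no alpha. SAP 6.3.1 is headed as covering the histological primaries. SAP 6.4.4.1 applies the section 6.3 adjustment to the primary analyses, while SAP 6.4.5, which holds the key secondary, specifies a stratified CMH test and does not mention 6.3. Protocol 16.7.1 orders the primaries only, and Table 4 is keyed to them alone. This is a fair reading and it supports the fix below. It does not settle the matter, because protocol 16.3.1 names the (key) secondary as controlled, and items c and d sit under the SAP heading on control of type I error.

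It can also be said that the Month 18 analyses are done, so exactly one combination of primary results has occurred. The documents do not say which, and if no primary was met at one of the doses there is no breach. That stands, and it makes the point conditional.

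Finally, the SAP does not use the word strong for its error control. Requiring the 0.05 to hold under every combination of true and false nulls is my reading of a budget given to all testing. Practical inflation is absent in six of the eight simulated cases.

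**Conclusion.** The point holds as a mainly formal inconsistency. In the four listed rows no positive level for the Month 18 key secondary fits within 0.05, because Table 4 passes the whole remainder to outcomes on primary success alone. It matters only if one of those rows occurred.

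A reader might infer that the plan runs at a type I error of 0.07. The documents do not support that. The figure is an upper bound for row 1 at an inferred level, and simulated error passes 0.05 only in extreme overlap cases at assumed rates. Nor is Table 4 miscalculated; its arithmetic is exact. A reader might also see a contradiction between Table 4 and SAP 6.3.2, where "OCA doses will be compared to placebo in a sequential closed gate-keeping manner using Type I error of 0.03". It is not one: SAP 6.3.1 and protocol 16.7 make 0.03 the base level, and 6.3.2 refers to Table 4 for the scenarios.

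**What to change.** In SAP 6.3.1, items c and d of both scenarios, state that the Month 18 key secondary tests are nominal and outside family-wise error control. Leave Table 4 unchanged. In SAP section 11, record the departure from protocol 16.3.1 and say that this status was set after the Month 18 analyses; the entry is needed because the SAP describes its updates as concerning End of Study. Make no controlled key secondary claim alongside an outcomes claim at recycled alpha.

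Do not offer the other repair, which carries alpha to outcomes only if the key secondary is rejected. It would total 0.05 if fixed in advance, but the key secondary result already exists. A sponsor choosing between the two rules by that result could keep the full outcomes alpha either way, and the inflation would return.

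The cost is small: Month 18 key secondary p-values become descriptive, and outcomes power is unchanged. As a clarification only, SAP 6.3.2 should give the level as 0.03 plus any carried alpha (Table 4).
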